9.6. Runtime

Since 20 January 2017.

9.7. Primary analyses

The diagnostic accuracy of fluid responsiveness assessed by changes in EtCO₂, heart rate and blood pressure compared to the PLR test.

The diagnostic accuracy of fluid responsiveness assessed by a PLR test without lowering the head of the bed compared to the standard PLR test.

9.8. Secondary analyses

The association between a temporary PEEP-increase and cardiac output in fluid responders and fluid non-responders.

The diagnostic accuracy of a temporary PEEP-increase compared to the standard PLR test.

10. Acute respiratory distress syndrome

10.1. Research question

What is the diagnostic accuracy of a B-profile measured with pulmonary ultrasonography compared to bilateral consolidations assessed on chest radiography for the diagnosis of acute respiratory distress syndrome (ARDS)?

10.2. Variable of interest

ARDS will be defined according to the Berlin ARDS criteria: 1) presence of acute hypoxemic respiratory failure defined by a PaO₂/FiO₂ ratio < 300 mm Hg and PEEP ≥ 5 cm H₂O; 2) onset within one week of clinical insult or worsening respiratory symptoms; 3) bilateral consolidations on chest radiography or CT-thorax.

10.3. Timing of measurement

During inclusion in basic study (one-time snapshot).

10.4. Additional exclusion criteria

Included patients with no pulmonary ultrasound or chest radiography measurements, patients after pulmonary transplantation

10.5. Sample size, power and detectable difference

Due to a set sample size we were able to estimate the precision of our estimate (i.e. the maximum marginal error). In our pilot data, the diagnosis of ARDS was 5.8%, and the presence of a B-profile had a sensitivity of 88.5% and a specificity of 64.5%. Based on pilot data of 446 included, a type-I error of 0.015 (with a corresponding Z-value of 2.17), and the abovementioned prevalence, sensitivity and specificity, the estimated maximal marginal error for sensitivity is 13.6% and 20.4% for specificity.

10.6. Runtime

Since 1 September 2015. The research questions and hypotheses were incorporated at 1 February 2016.

10.7. Primary analysis

The diagnostic accuracy of a B-profile assessed with pulmonary ultrasonography compared to bilateral consolidations assessed on chest radiography for the diagnosis of ARDS.

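### Sub-study 10 does not hold one reference standard: 10.5 scores the B-profile against full ARDS, 10.7 sets it against the radiograph, and the radiograph is part of the ARDS definition

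*SAP*

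**What the plan says.** Three sections of SAP Appendix 1, sub-study 10, bear on this.

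- Section 10.2 fixes the target condition: "ARDS will be defined according to the Berlin ARDS criteria". Three elements are required: "presence of acute hypoxemic respiratory failure" with a PaO₂/FiO₂ limit and a PEEP minimum; "onset within one week of clinical insult or worsening respiratory symptoms"; and "bilateral consolidations on chest radiography or CT-thorax".
- Section 10.5 gives the pilot inputs: "the diagnosis of ARDS was 5.8%, and the presence of a B-profile had a sensitivity of 88.5% and a specificity of 64.5" per cent, in 446 patients. With Z = 2.17 it states margins of 13.6% for sensitivity and 20.4% for specificity.
- Section 10.7 states the primary analysis: "The diagnostic accuracy of a B-profile assessed with pulmonary ultrasonography compared to bilateral consolidations assessed on chest radiography for the diagnosis of ARDS". The research question in 10.1 and the entry in Table 1 put it the same way.

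The sub-study text does not mention that the radiograph named in 10.7 is also the third element of the definition in 10.2.

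**The concern.** An accuracy study needs one index test and one reference standard, and the reference should not contain a test whose accuracy is being judged. Here the radiograph appears twice: as what the B-profile is set against, and as a component of the diagnosis. Section 10.7 can be read with the radiograph as a competing test or as the reference, and 10.5 uses a third arrangement, with full ARDS as the reference for the B-profile alone.

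Different readings give different two-by-two tables from the same patients. An analyst could follow the text faithfully and still choose among them after seeing the data, which is what Section 7 of the SAP says the plan is meant to prevent. The meaning of specificity also changes. Against full ARDS it depends partly on oxygenation, PEEP and timing, which no lung image can show.

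**Working it through.** **Inputs (10.5):** N = 446; ARDS prevalence 5.8%; B-profile sensitivity 88.5%, specificity 64.5%; Z = 2.17. I keep the plan's Z throughout, so that only the denominator changes.

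**1. Which reference do the 10.5 figures use?**
- ARDS cases: 446 × 0.058 = 25.9, so 26. Non-ARDS: 446 − 26 = 420.
- Sensitivity: 23/26 = 88.5%.
- Specificity: 271/420 = 64.5%, which leaves 420 − 271 = 149 false positives.

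Whole counts on these denominators match both percentages, so the figures fit the B-profile alone scored against full ARDS in all 446 patients.

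**2. Reproducing the margins.** Margin = Z × √(p(1 − p)/n).
- Sensitivity: 2.17 × √(0.885 × 0.115/25.87) = 13.6%. This reproduces the plan and confirms the ARDS count as the denominator.
- Specificity with the non-ARDS count: 2.17 × √(0.645 × 0.355/420.1) = 5.1%, not 20.4%.
- Specificity with the ARDS count: 2.17 × √(0.645 × 0.355/25.87) = 20.4%. The stated figure comes from the wrong denominator.

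**3. If the radiograph in 10.7 is a rival test for ARDS.** Every ARDS case has bilateral consolidations on radiograph or CT. Radiograph sensitivity is then 1 − c/26, where c is the number of cases that qualified on CT only. The SAP does not give c. Over an assumed range:
- c = 0: 100%
- c = 1: 96.2%
- c = 2: 92.3%
- c = 3: 88.5%, equal to the B-profile's 23/26
- c = 5: 80.8%

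Without CT-only cases, ultrasound cannot exceed the radiograph on sensitivity, whatever its quality. Radiograph specificity is not fixed this way. Consolidations in a patient who fails the oxygenation/PEEP or onset criterion are a false positive for the radiograph too. The SAP gives no figure for this.

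**4. If the radiograph in 10.7 is the reference.** The number of reference-positive patients is 26 − c + r, where r is the number of non-ARDS patients with bilateral consolidations on the radiograph. Neither c nor r is given. The 5.8%, 88.5% and 64.5% are tied to the 26 ARDS cases, so they are not the prevalence and accuracy for this reference, and the margins do not describe the 10.7 analysis.

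**5. What the 149 false positives contain.** They include any B-profile positives who have bilateral consolidations but fail only the oxygenation/PEEP or onset criterion. In those patients ultrasound agrees with the imaging criterion and is still scored as wrong. Their number is not given, so the effect on 64.5% cannot be computed.

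**The case against.** The strongest objection is that no contest between the two tests is planned. Elsewhere in the SAP, accuracy of one measure compared to another means that the second is the reference: sub-study 2 (2.1 and 2.7, the chest radiograph) and sub-study 9 (9.1 and 9.7, the PLR test). Section 10.5 gives accuracy for the B-profile only, and the sub-study plans no radiograph sensitivity or specificity. The Berlin definition does not contain the B-profile, so the B-profile figures in 10.5 carry no incorporation bias. Scoring a sign against a composite diagnosis in all patients is ordinary specificity for that diagnosis.

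Most of this stands. A reader might infer that the comparison is rigged for the radiograph, or that ultrasound can neither beat nor fairly match it. The document does not support that: the built-in advantage exists only on the rival-test reading and only for sensitivity, CT-only cases can offset it, and the non-imaging criteria count against both tests on specificity. A reader might also put a figure on the lost specificity, but any such figure needs an assumed share of the 149 who meet criteria 1 and 2.

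The objection does not clear the plan. If the radiograph is the reference, 10.7 and its own precision calculation use different references.

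It is also fair that Sections 2.2.3 and 7 defer sub-study SAPs to later documents, and that the opening of Appendix 1 calls sub-study conclusions explorative. That lowers the severity, but 10.7 already names the primary analysis that a later document would inherit.

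**Conclusion.** The point holds as an inconsistency in the reference standard, with incorporation bias on one of the two readings. Section 10.5 uses full ARDS. Sections 10.1 and 10.7 use radiographic consolidations, either as a rival test contained in the definition or as a reference that 10.5 does not use. Neither reading leaves 10.2, 10.5 and 10.7 consistent.

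Two sizes can be stated. Radiograph sensitivity against ARDS would be 100% less c/26, with c unknown. The specificity margin for the reference that 10.5 does use is 5.1% rather than 20.4%. The second rests only on the plan's own inputs. The effect of the oxygenation/PEEP and onset criteria on B-profile specificity is real in direction but cannot be quantified from the SAP. Severity is low to moderate: this is the primary analysis of an exploratory sub-study, and rewording settles it.

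**What to change.** Restate 10.1, 10.7 and the Table 1 entry as one like-for-like question: the accuracy of the B-profile against bilateral consolidations on radiograph or CT, among patients meeting criteria 1 and 2. The same question can be put as agreement between criteria 1 + 2 + B-profile and criteria 1 + 2 + radiograph/CT. If so, keep it within those patients, since patients failing criterion 1 or 2 would be automatic agreements and would raise specificity. Do not report radiograph accuracy against a definition that contains the radiograph.

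Then recompute 10.5 for the chosen reference and denominator. Under this restatement every ARDS case meets criteria 1 and 2, so 23/26 and its 13.6% margin carry over. Specificity must be recounted. If full ARDS in all patients is kept as a further analysis, label it as such and correct its specificity margin to 5.1%.

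The cost is wording plus some precision. Table 2 already lists ventilator settings, respiratory distress and ARDS risk factors for sub-study 10, and arterial blood gases for the basic study. The smaller denominator widens the specificity interval. As an illustration, if 25% to 75% of the 420 non-ARDS patients meet criteria 1 and 2 (an assumption) and specificity stays at 64.5%, n is 105 to 315 and the margin 2.17 × √(0.645 × 0.355/n) is 10.1% to 5.9%.

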10.8. Secondary analysis

The association between B-lines measured with pulmonary ultrasonography and clinical examination, biochemical and haemodynamic variables.

11. Myocardial strain

11.1. Research question

Are left ventricular (LV) and RV-myocardial strain measured with tissue Doppler imaging associated with 90-day mortality?

11.2. Variable of interest

Myocardial strain and myocardial strain rates have been measured with the cardiac probe M3S of M4S with default cardiac imaging setting of the General Electric Vivid-S6 mobile ultrasound machine. The measurements were obtained in the AP4CH window with a left ventricle and right ventricle centred view for left and right myocardial strain, respectively.

11.3. Timing of measurement

During inclusion in basic study (one-time snapshot).

11.4. Additional exclusion criteria

None.

11.5. Sample size, power and detectable difference

In a pilot study we included 51 patients of which 9 died. Pilot data from our design paper indicate that the 90-day mortality proportion among controls is 0.28⁷. We will be able to detect a true relative risk of 3.0 in diseased patients subjects relative to patients who survived with probability (power) 0.80. The Type I error probability associated with this test of the null hypothesis that this relative risk equals 1 is 0.015.

11.6. Runtime

Since 18 March 2017.

11.7. Primary analysis

The association between LV- and RV-myocardial strain measured with tissue Doppler imaging and 90-day mortality.

11.8. Secondary analyses

The association between LV- and RV-myocardial strain imaging and conventional CCUS measurements.

The level of agreement between myocardial strain measured with tissue Doppler imaging and myocardial strain rate measured with speckle tracking.
